9.6 Changes to the Protocol

No change in the Study procedures shall be effected without the mutual agreement of the Sponsor and the Principal Investigator. All changes must be documented as signed protocol amendments, or as a revised protocol. Changes to the protocol require notification to or approval by the IRB and the regulatory authorities before implementation. Local regulatory requirements must be followed.

The Sponsor is responsible for the distribution of protocol amendment(s) to the Principal Investigator(s) and those concerned within the conduct of the Study. The Principal Investigator is responsible for the distribution of all amendments to the IRB and all staff concerned at his/her center.

Appendix I: Background Information

1.0 Scientific Literature

Bioelectrical Properties of Living Tissue

By definition, electrical impedance is the ratio of the voltage difference to the current across a circuit or a body (Ohm's law), and conductance is the inverse of impedance (1/impedance). The dielectric properties of human cells and tissue are widely recognized and are essential for several diagnostic procedures currently in use, such as the electrocardiogram.^{xiii} Bioelectrical conductance is the basis for the monitoring of certain physiological processes such as "impedance plethysmography" for measuring blood volume or Electrical Impedance Tomography" (EIT) for assessing lung ventilation^{xiv xv}. Other examples include multi-frequency Bioelectrical Impedance Analysis (BIA) to measure the electrophysiological properties of cell membranes and related body tissues as a predictor of body weight, fat content, and extracellular and intracellular water in a wide range of medical conditions.^{xvi}

Bioconductance and Malignant Tissue

Several experimental studies have demonstrated that the electrical properties of cancerous tumors vary significantly from normal, nonmalignant tissue^{xvii}. The mechanism has been attributed to the high water and sodium content within cancerous tissues with movement of potassium, magnesium and calcium out of the cell^{xviii,xix}. Other possible contributors include not only altered membrane permeability but also changes in membrane composition, the nucleus to cytoplasm ratio as well as alterations in cellular composition and density^{xx-xxi}. Many of the published studies are in breast cancer. For example, one study examined a set of 120 *impedivity spectra* collected in breast tissue immediately after excision from 64 patients undergoing breast surgery^{xxii}. This investigation reported that no significant differences were found between groups of normal breast tissue and those consisting of benign pathology such as fibroadenomas. However, the bioelectrical properties of the carcinoma group differed from the normal and benign tissue groups^{xxiii}. *In vitro*, hepatic studies have found differential electrical conductivity changes between tumor and control tissue in a rat model^{xxiv}. Another *in vitro* study examined brain, breast, gastric and colon cancers that had been implanted in a nude mouse model, grown, and then excised for investigation of electrical conductance properties^{xxv}. This investigation found that all four cancerous tissues had conductance values that were clearly different from non-cancerous tissue^{xxvi}.

In summary, studies conducted at the cellular and tissue level (as well as on recently excised human tissue) have demonstrated differences in electrical conductivity associated with various disease states including cancer.

Bioconductance and Cancer Diagnosis

Many clinical investigations have examined the potential of using electrical properties to aid in cancer diagnosis. Electrical bio-conductance has been shown to successfully discriminate between cancerous and non-cancerous tissue for skin cancer,^{xxvii} cancer of the lymph nodes^{xxviii} and breast cancer^{xxix} and has shown promise as a screening tool for the detection of cervical^{xxx} and colorectal cancers^{xxxi}.

There is also growing evidence regarding differences in lung tissue bioconductivity associated with lung cancer.^{xxxii} In one non-invasive study of bioconductance measurement in lung cancer, bioelectric impedance vector analysis in patients with known advanced stage (IIIB and IV) lung cancer (66) was compared with healthy controls (56)^{xxxiii}. The conclusion drawn by Toso and colleagues is that a distinct difference in transcutaneous bioimpedance (a combination of resistance and capacitance) can be seen between patients with advanced lung cancer and normal controls, and that in the advanced cancer cohort, regardless of their measured Body Mass Index (or BMI, one commonly used index of nutrition), bioconductance measurement differences provided a better measurement of survival, and hence prognosis.

A second study utilized electrical impedance tomography to provide *in vivo* imaging prior to surgery in 22 patients with single sided lung cancer and 7 healthy subjects^{xxxiv}. These investigators found that “images” in 19 of the 22 affected lung cancer patients showed differences in conductivity that were statistically different from the average conductivity of a healthy lung.

In addition to these studies, the ProLung Test developed by Fresh Medical Laboratories has been examined in 3 clinical studies, which evaluated the feasibility of using a non-invasive bioconductance test to discriminate between malignant and non-malignant lung tissue.

2.0 Clinical Studies: ProLung Test

The initial feasibility study, FML-201, tested the ProLung Test to discriminate between the bioconductance measurements recorded for age-and gender-matched subjects with and without biopsy-confirmed lung cancer. The second study, FML-203, examined measurement reliability and reproducibility in a normal subject sample. The third, FML -204, tested the ProLung Test’s discriminatory ability in undiagnosed patients who exhibited lesions that were suspicious for lung cancer.

A. Feasibility Study (FML-201). McHenry IL 2007. The study’s first Specific Aim was to investigate ProLung Test effectiveness in discriminating between clinically symptomatic patients (n=18) with and without (n=18) lung cancer. The subjects were also evaluated for any adverse events connected with use of the test.

The study was a single-site, single-blind (i.e., ProLung Test operator and statistician were unaware of subject diagnosis), two-arm design with screening and bioelectrical conductance measurement visits. Biopsy was performed prior to conductivity measurement. Figure 1 below illustrates the performance of the optimal algorithm in this initial set of patients.

[figure not shown]

Figure 1. Discrimination of cancer from non-cancer patients.

Results. In the FML-201, the derived Algorithm was able to perfectly discriminate (vertical line) biopsy-confirmed cancer subjects from age- and gender-matched cancer-free subjects. X-axis: composite score units. Y-axis: study arm 1, non-cancer; study arm 2, cancer.

Conclusion. These data supported the hypothesis that trans-thoracic conductance measurements obtained using the ProLung Test distinguish statistically significant conductivity differences between cancerous and non-cancerous lung tissue in a small patient sample. This suggested feasibility of the technology. Further algorithm development with validation was planned for a subsequent larger study.

B. Reliability and Reproduceability Study (FML-203). The variability of repeated ProLung conductance measurements was investigated using a single ProLung unit and operator on 22 normal subjects over two days of testing at the Salt Lake Community College in Salt Lake City Utah. The Specific Aim was to investigate ProLung unit variability as estimated from repeated measurements on the same subject in succession.

Results. The maximum and minimum conductance results were comparable, with slightly lower standard deviations for maximum conductance readings and extremely high reliability indices for both measures. For both data sets, the same measurement points were found to have minimal variability (and maximal reliability) indices.

Conclusion. The results suggest a high degree of consistency in the ProLung measurements and support the reliability of this procedure as an adjunct to other methods used to risk-stratify patients who have suspicious lung lesions.

C. Transcutaneous Computed Bioconductance Measurement in Lung Cancer: A Treatment Enabling Technology Useful for Adjunctive Risk Stratification in the Evaluation of Suspicious Pulmonary Lesions

Methods. The research was conducted at Johns Hopkins School of Medicine, by members of the faculty at that institution and the University of Utah School of Medicine, as well as members of the Fresh Medical Laboratories clinical staff. The Study was published in the April 2012 edition of the Journal of Thoracic Oncology. The purpose of this Study was to further develop a mathematical algorithm that discriminates between benign and malignant pulmonary lesions found on spiral chest CT scans, using the noninvasive transcutaneous computed bioconductance (ProLung) measurement Test. The Study's hypotheses were (1) designed to assess the stability of the ProLung Test classification Algorithm when used as an adjunct

to CT scan, and (2) to assess whether there are any potential safety concerns of the ProLung Test when used to evaluate patients with a positive CT scan.

Subjects age 18 and above were recruited sequentially and randomly from those who were eligible and agreed to participate in the study, and were enrolled under an IRB-approved protocol (IRB # NA_00007789). All subjects presented with one or more suspicious radiological and/or clinical finding(s) for lung cancer, and all had undergone a CT scan of the lungs that indicated one or more non-calcified nodules (NCN) or lung masses suspicious for lung cancer, or the subjects were scheduled to receive a CT scan of the lung within 14 days of enrollment.

Forty-one patients were qualified to participate in the study. The statistical approach used an optimal cut-point methodology for classifying the two patient groups (malignant or non-malignant) based on the variables associated with the conductance measurements. The cut-point that provides the best test characteristics was considered the optimal cut-point.⁷²

Results: (Yung, 2012)^{xxxv xxxvi xxxvii}. Using this methodology for analyzing the ProLung's bioconductance test data for the 41 patients resulted in the scatter plot in Figure 2. As shown here, 11 of the 12 patients with benign lesions had composite scores that fell below the cut-point. For the malignant cases, 26 of the 29 had composite scores above the predetermined cut-off point with 3 falling below it. Computed bioconductance measurements discriminated between malignant lesions (29 primary lung cancers) and benign pathology (12) across a range of IPL sizes (0.8 cm and greater) with a sensitivity of 89.7% (positive predictive value 96.3%) and specificity of 91.7% (negative predictive value 78.5%).

Conclusion. This study found different bioconductance properties between cancerous and non-cancerous lung lesions and provides encouraging results for continued development of the ProLung Test.

[figure not shown]

Figure 2: Patient Bioconductance (ProLung) Test Results illustrate the composite scores for the benign patients (represented by the closed triangles) and the composite scores for the malignant cases (represented by the open squares) with reference to the Cutoff Point.

3.0 ProLung Unit: Technical Description

The ProLung unit measures bioelectrical conductivity at multiple points on the skin's surface. The probe introduces a low electrical current (too low to be felt) into the body and has adhesive electrodes that measure the current at other parts of the body. The ProLung unit is shown below in Figure 3 and has three functional components as illustrated in the schematic in Figure 4. The Measurement component includes both the hardware and software that obtain and record accurate and reproducible bioelectrical conductance measurements (data sets) of the thoracic cavity, referred to as the computerized bioconductance (ProLung) test output. All of the software, hardware and unit configurations provided to the investigatory team, as illustrated below, are proprietary to the Sponsor.

Figure 3. Fresh Medical Laboratories ProLung unit with probe (on left) and associated computer screen (on right) illustrating the Operator display.

[figure not shown]

Figure 4. ProLung Functional Components shown as a flow chart illustrating the sequence of function of the ProLung unit.

3.1 Classifier Algorithm Design and Function

With reference to Figure 4, above, following measurement, the characteristics of each subject's data set are recorded and validated. A ProLung data set or file consists of the measurements obtained at the

acquisition points for each subject. The classifier Algorithm then analyzes the data set. The algorithm processes specific properties of the data set to generate a report to aid the clinician in assessing the risk of malignancy associated with known lesions.

3.2 Classification

The ProLung report offers the test's conclusions regarding patients with lesions; 1) high risk for malignancy or 2) low risk for malignancy. With regulatory clearance, test results are to be used adjunctively with CT information and other risk factors to aid in the risk stratification of patients with indeterminate lung lesions that are suspicious for lung cancer.

3.3 Clinical Use

The ProLung unit is designed for ease of operation, service and reliable performance. The ProLung unit conforms with all applicable safety standards and has been designated as a *non significant risk device* in its previous IRB reviews. In preparation for investigational use, Fresh Medical Laboratories provides appropriate training. The ProLung provides screen prompts for essential subject information entry, and provides visual anatomic views to guide the operator through each measurement in the protocol sequence. The ProLung unit also provides visual and audible indications of measurement quality to the operator and the option of subject data measurement review by the operator.

3.4 ProLung Unit Physical Description

The ProLung unit measures 13.5" wide by 13.15" deep by 3.15" high and integrates proprietary hardware and a Microsoft Windows™-based computer system within the enclosure. Typical computer operator interface and peripheral equipment is attached to the device including mouse, display and keyboard. The proprietary diaphoretic electrodes and computer driven data acquisition probe are connected by cords to easily connect to matching color coded ports on the left side of the device body. The data acquisition probe uses a unique, single-use tip that makes contact with the patient's skin during the scan session. Marketed single-use kits will contain proprietary single-use tip and 6 (six) diaphoretic single-use adhesive reference electrodes. The patented probe design is critical to insure accurate and consistent measurements as described below. A printer may be attached to the system. The ProLung unit is a portable self-contained device.

3.5 Safety Information

The International Electrotechnical Commission (IEC) publishes the base standard 60601 that establishes limits for leakage current from a medical device at 150 microamps (0.000150 amps). The ProLung unit generates less than 10% of the allowable leakage current for medical devices. The instrument design includes industry approved isolation circuitry for use in clinical instrumentation.

The ProLung unit delivers a safe current of <25 micro amps to measure bioconductance between reference electrodes placed on the patient's back or hands and a computerized bioconductance probe placed sequentially at points on the skin surface. There is also safety information available from other currently marketed devices that introduce current into the body during usage. To cite two modalities, transcutaneous electrical nerve stimulation (TENS) and percutaneous electrical nerve stimulation (PENS)

are used for acute post-operative or chronic intractable pain^{xxxviii xxxix}. TENS is characterized by biphasic current and most TENS units produce a current of 1 to 80 microampere (mA), 9 V (average), 2 to 1000 Hz, with a pulse width of 250 to 400 microseconds. PENS uses needles as electrodes that are placed in soft tissues or muscles at dermatomal levels corresponding to the local pathology. A 5-Hz frequency with a pulse width of 0.5 mS is usually used. Another FDA-approved device that delivers electrical stimulation is the ReliefBand^R that is used to prevent or treat nausea and vomiting associated with motion sickness, pregnancy, or chemotherapy^{xl}. Thus, the amount of electrical current that is associated with use of the ProLung is negligible and has not been nor is it expected to be associated with health risks or discomfort.

## **Analysis Summary**

**Study Title:** A Multi-Center Trial of the ProLung Test (Transthoracic Bioconductance Measurement) as an Adjunct to CT Chest Scans for the Risk Stratification of Patients with Pulmonary Lesions Suspicious for Lung Cancer (Protocol PL-208)

**Primary Objective:** To demonstrate that the ProLung Test can assist in the assessment of patients presenting with indeterminant CT scans.

**Primary Endpoint:** The coprimary endpoints are the Positive Predictive Value (PPV) and Negative Predictive Value (NPV)

**Secondary Endpoints:** Co-secondary endpoints of sensitivity and specificity of the ProLung Test and the sum of PPV and NPV

**Additional Endpoints:** Additional Effectiveness Endpoint Analyses - Subgroup Analyses of NPV, PPV, sensitivity and specificity.

**Patient Population:** Males and females aged 18 years and older with a CT scan of the lungs that indicates one or more nodules or lesions suspicious for lung cancer.

**Study Design:** A single arm multicenter study of subjects with CT scans with nodules of undetermined significance and known diagnosis to be used to validate the ProLung Test to stratify the positive risk of lung cancer.

**Number of Patients:** 174 subjects with paired ProLung test result and a biopsy or radiological stability diagnosis for lung cancer.

# Statistical Procedures

---

## **I. Introduction**

Lung cancer is the deadliest form of cancer, with a 5-year survival rate in the United States of 16% (Jemal, Ahmedin et al. (2010)). Currently, it is difficult to detect and diagnose lung cancer early enough for treatment to be effective. New, immediate, and non-invasive methods are needed to stratify the risk of this disease in its earliest stages. Bioconductance technology of ProLung Inc. (formerly Fresh Medical Laboratories) has demonstrated the potential to meet these requirements.

The current standard of care for the detection of lung cancer involves the use of CT chest scans to evaluate patients with lesions suspicious for lung cancer. While these scans provide important information about the location and size of lung lesions and raise suspicion of lung cancer, they have limited capacity to determine immediately the malignant or benign nature of the lesions they identify. In the screening setting, between 23% to 33% of all CT screens are “positive” for an indeterminate nodule; among these 94% of non-calcified nodules are determined to be benign (Aberle et al. (2011)). This presents a significant diagnostic challenge (Black (2000) and Welch and Black (2010)). Given the frequency of benign diagnosis, routine biopsy in an indeterminate lesion cannot usually be clinically justified. Because of these constraints, current guidelines (McMahon et al. (2017)) call for repeated CT scans over a period of months or years, in order to detect malignant growth in the detected lesion(s).

## **II. Study Design**

This Study is a prospective cohort, single arm, multicenter study of subjects with indeterminate CT scans with known biopsy results or a follow-up CT scan showing radiological stability to be used to validate the ProLung Test to stratify the positive risk of lung cancer. The validation subjects are from the second phase of a two-part study to: 1) define the algorithm for cancer detection, i.e. the stabilization phase for algorithm development and cutoff determination and 2) the validation phase to evaluate the risk stratification. No subjects used in the validation portion of the study were used in the algorithm optimization.

## **III. Analysis Objectives**

The primary Study hypothesis is that the ProLung Test will demonstrate safety and effectiveness in the PPV and NPV of patients with pulmonary lesions identified by CT that are suspicious for lung cancer. A statistically significant result will indicate that patients with a positive ProLung Test result will have a clinically relevant PPV.

## **IV. Analysis Populations**

### **A. Intent-to-Treat (ITT) Population**

The intent-to-treat population is every subject that is enrolled in the study.

### **B. Completed Cases (CC) Population**

All subjects that have paired results of both ProLung Test and either confirmatory tissue biopsy (of cancer or benign condition) or radiologic stability to infer a benign diagnosis.. The primary and secondary analyses require paired evaluations and therefore will be conducted in the completed cases population.

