3.0 Study Design

This Study consists of two distinct phases, Stabilization and Validation. The Study will collect data from multiple sites (3 to 20), and each site may enroll patients and collect data for the Stabilization and Validation Phases with a minimum of three sites for the Validation Phase. In this multi-center Study, the patient's known diagnosis (of either a malignant or benign outcome) will be compared to the ProLung Test results. The patient's diagnosis is determined by tissue biopsy, surgical resection or by CT follow-up detecting significant nodule growth during a 1 year time frame. This Study follows the National Comprehensive Cancer Network definition for nodule growth. Nodule growth is defined as: 1) for nodules 15 mm or smaller: an increase in mean diameter of 2 mm or more in any nodule or in the solid portion of a part-solid nodule when compared with the baseline scan, or 2) for nodules 15 mm or more: an increase of 15% in mean diameter when compared with the baseline scan. Mean diameter is the mean of the longest diameter of the nodule and its perpendicular diameter^{xii}. If no significant growth is detected and the nodule is not definitively diagnosed by biopsy or surgical excision, the outcome will be considered benign unless indicated otherwise in the patient's medical record.

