4.0 Subject Selection and Participation

4.1 Inclusion Criteria

Subjects who meet all of the following criteria may be enrolled in this Study:

1. Subject is male or female, age 18 or older.
2. Subject has undergone CT scan of the lung(s) that indicates one or more nodules or lesions suspicious for lung cancer.
3. Subject’s pulmonary nodule or lesion is greater than 4mm. Size is determined by the largest nodule or lesion dimension identified from CT imaging.
4. Subject meets one or more of the following conditions:
 - indicated for a tissue biopsy

- indicated for surgical resection of the lung
- 5. Subject must be able to receive a ProLung Test
 - within 60 days of abnormal CT (*Inclusion Criterion 2 & 3*)
 - within 60 days prior to the tissue biopsy or surgical resection (*Inclusion Criterion 4*).
- 6. Subject is capable of understanding and agreeing to fulfill the requirements of this Protocol.
- 7. Subject has signed the IRB/IEC approved Informed Consent Form ("ICF").

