4.3.1 Events Necessitating Premature Discontinuation

The occurrence of any one of the following events may necessitate premature discontinuation of a subject from the Study:

- Subject develops any of the exclusion criteria after enrollment.
- Subject is unwilling to continue in the Study.
- Subject does not comply with the Study Protocol.
- Subject being followed by CT for nodule growth who does not receive a follow-up CT by their 1-year enrollment anniversary or within 60 days after their 1-year enrollment anniversary.

- Principal Investigator decision.

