5.10 Follow-up Outcome Assessment

The outcomes of any ancillary diagnostic procedures conducted as part of normal clinical care will be collected for further analysis and the provided CRF page(s) will be completed as appropriate. The Study participant will sign a "Release of Medical Information" at the time of the consent process. All laboratory and radiological tests performed to further evaluate the abnormal chest CT will be obtained by the study team and kept as part of the participant's source document. This will include but are not limited to results of biopsies, sputum cytology, repeat chest CT scans, repeat chest radiography, MRI and PET scans.

Prior to the close of the Study, each site will obtain the most recent CT Report and History and Physical (if available) for all enrolled subjects who received a benign biopsy result or a CT follow-up showing stability to re-confirm that the subjects have remained free of malignancy.

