With respect to determining the optimal sample size of the Validation Phase, it is assumed that the sensitivity of the ProLung test (probability of having had a high risk test among subjects who subsequently had a malignant biopsy) is 70% and that the specificity (probability of having had a low risk test among subjects who subsequently had a benign biopsy) is also 70%. It is further assumed that among the patient population studied in this Study, approximately 70% will have a malignant biopsy. Based on these assumptions, 88 subjects will provide 90% power to reject the primary null hypothesis. The primary analysis will only include subjects who have a biopsy within 60 days of their ProLung test and have a definitive biopsy result. Subjects who fail to have a biopsy or do not have a definitive biopsy result will be excluded. To account for as many as 12% of such subjects, 100 subjects will be enrolled into the Validation Phase. Furthermore, to maintain the Study's statistical power, enrollment will continue until there is both a minimum of 100 subjects and a minimum of 40 ProLung high risk and a minimum of 40 ProLung low risk subjects are enrolled.

The primary null hypothesis is that the relative risk of a malignant biopsy among subjects with a high risk ProLung test result to that of subjects with a low risk ProLung test result is 1.0, vs. the alternative hypothesis that the relative risk is different from 1.0. This hypothesis will be tested by a two-sided Fisher's Exact Test at the 5% level of significance. If the relative risk is found to be greater than 1.0

($p < 0.05$), it will be concluded that subjects with a high risk ProLung test result are prognostically at greater risk to have a malignant biopsy than subjects with a low risk ProLung Test result. The relative risk will also be presented with its approximate 95% confidence interval.

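### Protocol 8.1 limits the primary analysis to biopsied subjects; SAP IV.B adds subjects called benign on CT stability, gives CT growth no route to malignant, and neither text says which rule governs

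*SAP*

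**What the plan says.** Protocol 8.1 is explicit: "The primary analysis will only include subjects who have a biopsy within 60 days of their ProLung test and have a definitive biopsy result". It continues: "Subjects who fail to have a biopsy or do not have a definitive biopsy result will be excluded".

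SAP IV.B places the primary and secondary analyses in the completed cases population, defined by a ProLung result paired with "either confirmatory tissue biopsy (of cancer or benign condition) or radiologic stability to infer a benign diagnosis". The SAP's Analysis Summary and Section II repeat the biopsy-or-stability definition. The SAP does not restate the 60-day window.

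Other parts of the protocol also use CT outcomes:

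- Section 3.0 lets the diagnosis be determined "by CT follow-up detecting significant nodule growth during a 1 year time frame", and in the other direction: "If no significant growth is detected and the nodule is not definitively diagnosed by biopsy or surgical excision, the outcome will be considered benign".
- Section 4.3.1 lists, among events that may require discontinuation, a "Subject being followed by CT for nodule growth who does not receive a follow-up CT by their 1-year enrollment anniversary" (or within 60 days after it).
- Section 5.10 asks sites, before study close, to review subjects with a benign biopsy or "a CT follow-up showing stability to re-confirm that the subjects have remained free of malignancy".

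SAP X.B defines sensitivity among subjects with a positive biopsy, and specificity among subjects with a negative biopsy or a CT follow-up result. SAP V.A.1 gives 111 malignant and 63 benign subjects without saying how each diagnosis was reached.

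**The concern.** An unbiopsied subject with a stable CT is excluded under Protocol 8.1 and counted as benign under SAP IV.B. Both rules cannot be followed. Section 8.1 is the outlier within the protocol, but the supplied text does not say that the SAP replaces it.

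The SAP's CT route also runs one way. Read as written, stability brings a subject in as benign, while growth in an unbiopsied nodule has no place in the completed cases set, although Protocol 3.0 treats growth as determining the diagnosis. Admitting CT-benign subjects without a matching route for cancers lowers prevalence, which raises NPV and lowers PPV. Both are co-primary, both must succeed, and both goals were set for the 111/63 split. A reader therefore needs to know who makes up the 63, and whether growth cases are among the 111.

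**Working it through.** **The plan's own figures.** Protocol 8.1 assumes sensitivity, specificity and prevalence of 0.70.

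- P(high risk) = 0.70×0.70 + 0.30×0.30 = 0.58.
- Malignancy risk is 0.49/0.58 = 0.845 after a high-risk result and 0.21/0.42 = 0.500 after a low-risk result.
- The continuity-corrected two-proportion formula (two-sided 0.05, power 0.90, allocation 0.58/0.42) gives 88 subjects, and 88/0.88 = 100. Both match the protocol.

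That sample size is built on a biopsy-only set. The SAP's 174 subjects (prevalence 111/174 = 0.638) are built on biopsy plus CT stability.

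**Inputs for the SAP tests.** SAP V.A.1 gives expected cells of 78 TP, 33 FN, 22 FP and 41 TN, and goals of 0.638 (PPV) and 0.381 (NPV). SAP X.A specifies a one-sided exact binomial test at 0.025. Let k be the number of CT-stable-only subjects among the 63 benign. The documents do not give k, so it is an assumption throughout.

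**NPV test when CT-stable subjects are removed, goal held at 0.381**

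| True negatives removed | NPV | p | Lower limit | Result |
|---|---|---|---|---|
| 0 | 41/74 = 0.554 | 0.0019 | above goal | pass |
| 7 | 34/67 = 0.507 | 0.0236 | 0.382 | pass |
| 8 | 33/66 = 0.500 | 0.0325 | 0.374 | fail |

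What k this implies depends on how the CT-stable subjects tested:

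- All true negatives: k = 8.
- Average specificity, 41/63 = 0.651: 8/0.651 is about 12 (8 TN and 4 FP removed).
- All 22 false positives CT-stable: k = 29 (22 + 7) still passes and k = 30 (22 + 8) fails.

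At k = 12, prevalence moves from 0.638 to 111/162 = 0.685, NPV from 0.554 to 0.500, and PPV from 78/100 = 0.780 to 78/96 = 0.813.

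**NPV power, goal held at 0.381.** Exact enumeration with TP ~ Bin(111, 78/111) and TN ~ Bin(63−k, 41/63), so the number of negative tests varies:

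| k | 0 | 5 | 8 | 10 | 12 | 15 |
|---|---|---|---|---|---|---|
| Power | 0.910 | 0.775 | 0.651 | 0.555 | 0.453 | 0.304 |

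Fixing the number of negative tests at its expected value gives about 0.85, 0.72 and 0.37 at k = 0, 5 and 15. The level depends on the sampling model; the steep fall does not.

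**Goals re-derived for the smaller set.** These are the highest goals, on a 0.001 grid, that keep the k = 0 power (NPV 0.910, PPV 0.930):

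| k | NPV goal | PPV goal |
|---|---|---|
| 8 | 0.342 | 0.661 |
| 12 | 0.322 | 0.673 |
| 15 | 0.306 | 0.683 |

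Joint power is then 0.905 to 0.909.

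**Protocol's Fisher test.** At the expected cells, two-sided p = 0.000007 at k = 0 and 0.00003 at k = 12; power is 0.995 and 0.988.

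**Growth cases added as malignant.** Ten added false negatives give 41/84, p = 0.029, lower limit 0.377, a fail; nine still pass. At the average miss rate of 33/111, ten false negatives need 10/(33/111), about 34 growth cases.

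**The case against.** The SAP is clear about its own primary set. The two sets also belong to different primary analyses: the protocol tests relative risk by Fisher's exact test, while the SAP tests PPV and NPV against goals. The NPV failure comes from a hybrid that neither document prescribes, namely the protocol's population with the SAP's test and a goal set for another case mix. In addition, k may be small, because inclusion criterion 4 requires every subject to be indicated for biopsy or resection. All of this stands, and it limits the figures above to illustration.

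On growth, biopsy may be shorthand for any tissue diagnosis. Resection, too, is listed separately in Protocol 3.0 and missing from SAP IV.B. The asymmetric wording in SAP X.B concerns endpoints that are not hypothesis-tested. That is a fair reading, but the text does not settle it, and SAP IV.B itself admits CT evidence only for a benign diagnosis.

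The missing 60-day window is a minor gap, since inclusion criterion 5 already asks that subjects can be tested "within 60 days prior to the tissue biopsy or surgical resection". Title and signature pages were not available, so the absence of a precedence statement applies to the supplied text only.

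None of this removes the contradiction. Protocol 4.3.2 adds to it: its list of events removing subjects from the primary analyses includes an inconclusive biopsy but not the absence of one.

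**Conclusion.** The concern holds and should be fixed. Protocol 8.1 and SAP IV.B define different primary populations, and the SAP's CT route as written can add benign subjects only. The effect falls on the SAP's PPV and NPV tests; the protocol's Fisher conclusion at the expected cells does not depend on it.

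The size rests on k. It is nil at k = 0. With the NPV goal left at 0.381 and the expected cells, the biopsy-only NPV result changes at k of 8 to 30 depending on how those subjects tested, and at about 12 under average specificity. For scale, 12/174 is 6.9%, while Protocol 8.1 allowed up to 12% without a biopsy or a definitive result. That allowance also covers inconclusive biopsies, so it is not an estimate of k. Growth cases alone are unlikely to change the NPV result. The finding does not show that the SAP's population is wrong or that the trial would fail.

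**What to change.** Make these changes before ProLung results are linked to diagnoses. The documents do not say whether that has already happened; if it has, date and label the changes accordingly.

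1. Reconcile Protocol 8.1 (with 4.3.2) and SAP IV.B to one primary population, and state whether the 60-day window applies.
2. Align SAP IV.B and X.B with the growth definition in Protocol 3.0, so that CT follow-up can yield either outcome, and state whether the 111 already include growth cases.
3. Report the number of CT-stable-only subjects among the benign, split by ProLung result.
4. Prespecify PPV and NPV in the biopsy-within-60-days set as a sensitivity analysis. If that set becomes primary, re-derive both goals for its case mix.

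The cost is wording in two documents, one extra count, and the same tables re-run on data already collected. The downside is that NPV in the biopsy-only set may look less favourable, while PPV would look better.
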